10.3 What data will be collected, including long-term follow-up?

The following data will be collected in this study:

- visual acuity
- contact lens comfort questionnaire
- keratograph surface evaluation (tear break up score)
- ocular surface staining
- contact lens fitting characteristics (apical clearance, limbal clearance, scleral landing evaluation)

11.0 Setting

11.1 Describe the sites or locations where your research team will conduct the research.

Page 14 of 22 Revised: July 24, 2017

Subjects will be asked to complete measurements at the study visits, which will be conducted in clinical research facilities associated with the University of Houston College Of Optometry. The study visits will take place in The Ocular Surface Institute's research exam rooms in the Health and Biomedical Sciences Building (HBSB).

12.0 Drugs or Devices

Corneal and Scleral lenses are considered class II medical devices by the FDA. All rigid lens materials are FDA approved for use in a rigid contact lens, they are not investigative devices. All lenses will be stored in room 236 of the HBSB at UHCO until time of dispense to the subjects, and only study investigators will have access to the lenses.

The Tangible Boost Replenishing system is not yet FDA approved but is undergoing approval, and the ingredients are all classified under the GRAS (generally recognized as safe) designation through the FDA. The boost system contains the same ingredients as the Hydra-PEG coating that it is designed to replenish. The HydraPEG coating has received approval for use with rigid contact lenses. Full product information regarding the Tangible Boost system, as well as correspondence with the FDA is in the appendix.

13.0 Risks to Subjects

13.1 List the reasonably foreseeable risks, discomforts, hazards, or inconveniences to the subjects related the subjects' participation in the research. Include as may be useful for the IRB's consideration, describe the probability, magnitude, duration, and reversibility of the risks. Consider physical, psychological, social, legal, and economic risks.

Contact lens subject risks are those that are already associated with wearing a contact lens. These risks include developing an abrasion ('cut' on the eye) during lens application or removal, excessive debris accumulation on or beneath the lenses, ocular stinging, redness, itching, or irritation. All contact lens wearers are at risk for developing inflammatory and/or infectious complications during lens wear, but there is no added risk by participating in this study. There are no unforeseeable risks that the investigators can imagine with any of the procedures in this study.

13.2 Describe procedures being performed to monitor subjects for safety

If a subject experiences an adverse event during the duration of the study, they will be instructed to call the study coordinator who will communicate with the investigators to determine the best course of action. If the subject needs to be seen due to an adverse event, a study investigator will examine them and the customary procedure for management will be followed.

Page 15 of 22 Revised: July 24, 2017

13.3 Describe procedures performed to lessen the probability or magnitude of risks.

The investigators will be instructing subjects on the proper handling and care of their lenses, and will instruct the subjects of symptoms of an adverse event and who to call in that case (the coordinator). If an adverse event such as an abrasion occurs during a study visit, the condition will be treated as it is customarily, and the fees associated with treatment will be covered by the study.

14.0 Potential Benefits to Subjects

14.1 Describe the potential benefits that individual subjects may experience from taking part in the research. Include as may be useful for the IRB's consideration, the probability, magnitude, and duration of the potential benefits.

There is no direct benefit to the subject in participating in this study.

15.0 Provisions to Monitor Data to Ensure the Safety of Subjects – N/A

16.0 Withdrawal of Subjects

16.1 If applicable, describe anticipated circumstances under which subjects will be withdrawn from the research without their consent.

Subjects will be withdrawn from the study if they are unable to complete the tasks in the study protocol. In addition, if they experience an adverse event in which the investigator does not feel that the subjects should continue wearing the scleral lenses, they will be withdrawn.

16.2 Describe any procedures for orderly termination.

If a subject is terminated from the study prior to completion, they will still be compensated with the gift cards at the end of each study visit that they attend. They will not be compensated with gift cards for study visits that they do not attend.

16.3 Describe procedures that will be followed when subjects withdraw from the research, including partial withdrawal from procedures with continued data collection.

Page 16 of 22 Revised: July 24, 2017

The data from a subject that withdraws or is terminated from the study will not be included in the analysis.

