5.0 Number of Subjects

LOCAL:

5.1 Indicate the total number of subjects to be accrued locally.

A maximum of 40 subjects will be enrolled in this pilot study.

5.2 If applicable, distinguish between the number of subjects who are expected to be enrolled and screened, and the number of subjects needed to complete the research procedures (i.e., numbers of subjects excluding screen failures.)

We expect about a 20% screen fail/drop out rate, so will expect to recruit approximately 35-40 subjects, and the first 30 to be eligible and complete the study will be used for data analysis.

5.3 If not provided in the "study-wide" section, provide justification for the number of subjects. A power analysis is required for research that is more than minimal risk.

Page 6 of 22 Revised: July 24, 2017

This is a low risk study; there are limited data collected in other studies on rigid lens wear with the HydraPEG coating, so the data collected in this preliminary study will be used for future power calculations for larger studies. We chose 30 subjects to allow for an increased likelihood of reaching significance values with a moderate sample size. Further studies with larger sample sizes will likely be indicated if variability is high among the outcomes.

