10.0 Procedures Involved

10.1 Describe and explain the study design.

Once a subject has been identified, the initial visit will be scheduled. During the experimental day, informed consent will be completed, and the subjects will complete the following tasks: (1) an investigator will conduct visual acuity assessments of both eyes (Snellen). (2) The subjects will be asked to complete a survey (on contact lens satisfaction). (3) After the survey, the subject will sit with their lenses for assessment using the Keratograph topographer. (4) After topography, slit lamp assessment of the rigid lenses, and then of the cornea and conjunctiva (after lens removal) with and without Lissamine Green staining will be done.

At visit one, the following additional task will be performed: (1) The subject will be asked to sit for a corneal or scleral lens fitting visit (based on what they wear habitually), where the investigator will fit the subject with a commercially available scleral or corneal lens. All subjects will be refit into the Advanced Vision Technologies (AVT) brand of rigid lenses, manufactured at AVT Technologies in Colorado. If they already wear the AVT brand, the lens parameters will simply be re-ordered. All lenses will undergo a diagnostic fit with an AVT lens. The parameters available at AVT are similar to those available at all other major labs in the US.

A second visit will be to evaluate the fit of the ordered study lenses (which will have been coated with the HydraPEG coating), and will be for the dispense of the lenses. In addition to evaluating the lenses, the subjects will be asked to complete a short survey on their satisfaction with their current lenses. After this visit, the subjects will then wear the lenses for 30 days, on a daily basis as they habitually would, cleaning the lenses with ClearCare hydrogen peroxide cleaning system, a commonly used commercially available soft and rigid contact lens cleaner. After 30 days of lens wear, they will report for visit 3.

At the third visit, the same testing will be performed from visits 1 and 2, the subject will also be given an additional survey regarding the satisfaction with the HydraPEG lenses, and then the Tangible Boost kit or the placebo kit (consisting of

Page 9 of 22 Revised: July 24, 2017

two vials with Unique pH) solutions will be dispensed (randomized) to store their lenses in for 30 minutes that night.

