The solution will be dispensed and the subjects trained on its use, and the subjects will be asked to store their lenses in the given solution for 30 minutes that evening, and then transfer their lenses to Unique pH multipurpose rigid lens solution for overnight storage. For the initial training with the Boost or placebo system, the users will undergo an approximately 60-minute user training in which there will be visual and audio recording and still photographs taken in order for a human factors company (Userwise) to analyze the usability of the product. The investigator at the study visit will act as the monitor for the training session. This recorded training step was specifically designed to allow for proper evaluation of the usability of the product, which they will report to the FDA to ensure usability. At the initial visit, the subject will have indicated on the informed consent form whether they agree to participate in the recorded portion of the training. If they do not participate in the recording, they can still be trained and participate in the study.

The subjects will report to the Ocular Surface Institute the next day for Visit 4, at which time the comfort and visit tests will occur again, and an additional survey to evaluate the boost treatment will be given. After visit 4, the subjects will continue to wear the study lenses daily for an additional 60 days, treating their lenses again in the Boost or placebo solution at the midpoint between visit 4 and 5 (30 days after the first treatment with Boost), otherwise cleaning nightly with ClearCare, and will then report to the clinic again 30 days after the midway treatment (approximately 90 days after the initial HydraPEG dispense). The same visit testing will be done at this final and 5th visit, and a final short survey will be done, and then the lenses will be collected from the subjects and sent back to Tangible Science, Inc. for their internal testing of the lenses (no involvement of the UH research team). At this time the study will conclude.

The following table outlines each of the study visits and tells what procedures will be done at each visit:

Procedure	Length of Time Required for	Frequency of Repetition
VISIT 1: Initial Evaluation		
Informed consent & HIPAA	35 minutes	Once
General History and medications	5 minutes	Once per visit
Visual Acuity	5 minutes	Once per visit

Page 10 of 22 Revised: July 24, 2017

Questionnaires (CLDEQ8 + VAS)	10 minutes	Once per visit

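### Analysing only subjects who complete leaves out randomised subjects who withdraw, including for adverse events, and can bias the Boost–placebo and pre/post comparisons

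*Combined protocol and SAP*

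**What the plan says.** Two rules define the analysis set. Section 5.2 states that "the first 30 to be eligible and complete the study will be used for data analysis". Section 16.3 adds, without exception: "The data from a subject that withdraws or is terminated from the study will not be included in the analysis".

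Section 16.1 gives two grounds for withdrawing a subject: inability to carry out the study tasks, and "if they experience an adverse event in which the investigator does not feel that the subjects should continue wearing the scleral lenses".

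Section 10.1 sets the timing. Coated lenses are dispensed at Visit 2: "After this visit, the subjects will then wear the lenses for 30 days, on a daily basis as they habitually would". At Visit 3 the Boost or placebo "solutions will be dispensed (randomized) to store their lenses in for 30 minutes that night". Visit 4 is the next day, and after it "the subjects will continue to wear the study lenses daily for an additional 60 days", up to Visit 5.

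On attrition, section 5.2 says only this: "We expect about a 20% screen fail/drop out rate". Section 5.3 says that "the data collected in this preliminary study will be used for future power calculations for larger studies".

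The documents define no all-randomised analysis set, no method for missing visits, no sensitivity analysis and no exception for measurements taken before withdrawal.

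**The concern.** Randomisation makes the arms comparable at Visit 3. Restricting the analysis to those who reach Visit 5 replaces the randomised groups with groups selected by what happened over the next 60 days. A subject who leaves in that period already has Visit 3 measurements, and usually Visit 4 measurements. The records are kept, but section 16.3 bars them from the analysis.

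The selection is plausibly related to outcome. Section 13.1 lists abrasion, stinging, redness and irritation as risks, section 16.1 allows withdrawal for adverse events, and section 9.1 makes comfort and ocular surface staining primary endpoints. Those removed may be those doing worst.

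Three results are exposed:
- The Boost–placebo comparison, if outcome-related loss differs between arms. This applies to descriptive arm summaries as much as to a test.
- The pre/post comparisons, if loss is outcome-related, even when it is equal in both arms.
- The variance passed on to the power calculations in section 5.3, which looks too small if poor scorers are trimmed.

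**Working it through.** **1. The plan's own figure.** To obtain 30 completers at 20% combined loss: 30 / (1 − 0.20) = 37.5, so 38, inside the stated 35–40. Recruiting 35 gives 35 × 0.8 = 28 completers and recruiting 40 gives 32, so the first-30 rule alone drops at most about 2 completers. The 20% combines screen failure and drop-out, so the number lost after Visit 3 cannot be extracted. Of 35–40 recruits, 5–10 are not analysed, and anywhere from none to all of those could have been randomised.

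**2. Between-arm bias (illustration).** These inputs are assumptions, because the plan gives no allocation ratio, SD, significance level or named between-arm test: standard normal outcome, no true effect, 17 v 17 randomised, 3 lost in one arm and 1 in the other (14 + 16 = 30 analysed), two-sample t-test with 2.5% in each direction.

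The three lowest of 17 standard normal values have expectations −1.794, −1.319 and −1.029, which sum to −4.142.
- Arm losing its 3 worst: mean of the remainder = 4.142 / 14 = 0.296.
- Arm losing its 1 worst: 1.794 / 16 = 0.112.
- Bias = 0.296 − 0.112 = 0.184 SD.
- If drop-out correlates ρ with outcome, multiply by ρ. At ρ = 0.5: 0.092 SD. At ρ = 0: none.

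Simulation (100,000 runs per case):

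| Drop-out correlation | Bias (SD) | False result favouring the arm with more losses |
|---|---|---|
| 1 (worst scorers leave) | 0.19 | 10.4% (10.6% in a separate run) |
| 0.5 | 0.09 | 4.6–4.7% |
| 0 | 0 | 2.5% |

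Swapping the losses to 1 v 3 reverses the sign.

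**3. Equal losses (2 v 2).** There is no between-arm bias, but the pooled variance falls to about 0.72 of its true value if the worst leave (28% too low), or 0.93 at ρ = 0.5 (7% too low). Required sample size is proportional to variance, so a later study sized on it would be too small by the same share.

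**4. These are not upper bounds.** Take an exponential tail towards poor scores and let the worst scorers leave. Losing 4 from one arm and none from the other (15 v 15 analysed) gives 0.39 SD, against 0.35 SD for a normal outcome. Losing 2 v 2 of 17 cuts the variance by about 63%. Staining grades need not be normal.

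**5. What using the withheld data would recover.** Take 17 v 17 with 3 v 1 lost after Visit 4 and a correlation of 0.5 between any two visits. Fit Visit 4 on arm and Visit 3 in all randomised subjects (arm coefficient b4). Fit Visit 5 on arm, Visit 3 and Visit 4 in those who have Visit 5 (arm coefficient b5, Visit 4 slope c). The all-randomised estimate at Visit 5 is b5 + c·b4.

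| Drop-out depends on | Completer bias (SD) | All-randomised bias (SD) |
|---|---|---|
| Visit 4 score, worst leave | 0.095 | about 0 |
| Unseen Visit 5 score, worst leave | 0.18 | 0.13–0.14 |
| Unseen Visit 5 score, ρ = 0.5 | 0.09 | 0.06–0.07 |

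The coefficient b5 alone is not a substitute. It uses completers only and adjusts away effect already present at Visit 4. With a true effect of 0.5 SD at both visits, c = 0.5 / 1.5 = 0.333, so b5 = 0.5 × (1 − 0.333) = 0.33, whereas b5 + c·b4 = 0.33 + 0.333 × 0.5 = 0.50.

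**The case against.** The strongest reply is that this is a low-risk pilot in established lens wearers. Loss after Visit 3 may be zero, and if it is, or if it is unrelated to outcome, the rule does no harm. That stands, and it limits the weight of the point. It does not remove it, because section 25.1 plans hypothesis testing and section 5.3 carries the data forward.

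A second reply is that most of the calculated bias comes from the missing data, not from the rule. That also largely stands: where drop-out depends on the unseen Visit 5 score, rewording the rule recovers only part of the bias.

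A third is that section 10.2 treats the comparison with and without Boost descriptively and names no between-arm test. This is true, but the same selection distorts arm summaries.

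A reader might also infer several stronger things that the documents do not support:
- That the rule favours Boost. Nothing says which arm would lose more, and the bias follows the losses.
- That 20% of randomised subjects will be lost. The figure is not split.
- That data are destroyed. Section 25.1 keeps all study data for at least 3 years.
- That section 25.1 contradicts section 16.3 because it speaks of all collected data. It is general wording, and section 16.3 is the specific rule.
- That subjects who leave before Visit 3 damage the randomised comparison. They were never randomised. They matter only for comparing habitual with coated lenses, and having no Visit 3 value they cannot enter a paired Visit 1–3 test under any rule.

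**Conclusion.** The concern holds as a statement of what can happen under the written rule. Sections 5.2 and 16.3 make the Boost–placebo analysis set depend on post-randomisation events, no other section makes an exception, and one stated ground for withdrawal is close to two primary endpoints. Bias between arms needs withdrawal that is both outcome-related and different by arm. Bias in pre/post results and in the variance needs only outcome-related withdrawal.

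The actual size is unknown and may be zero. The illustrative 0.09–0.18 SD rests on normal outcomes, an assumed 17 v 17 split and assumed 3 v 1 losses. It is neither an estimate for this trial nor a ceiling. The rule should be changed, but it does not invalidate the study.

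**What to change.** Replace the analysis-set rules in sections 5.2 and 16.3:

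- **Boost v placebo:** analyse every subject randomised at Visit 3 in the assigned arm, with all Visit 3–5 measurements obtained, by a method that keeps subjects without Visit 5. An example is a repeated-measures model with Visit 3 as baseline and Visits 4 and 5 as outcomes. A Visit 5 regression adjusted for Visit 4 does not do this. Keep completers beyond the thirtieth.
- **Pre/post comparisons:** use every subject dispensed study lenses who has both visits being compared. For habitual v coated lenses at Visit 3, this recovers those who leave after Visit 3. For those who leave before it, report the number and reasons.
- **Sensitivity:** keep the completer analysis in this role and add one analysis that allows for outcome-related withdrawal, such as worst-rank scores. That method penalises the arm with more losses whatever the reason, so it should not be primary.
- **Reporting:** tabulate withdrawals with reasons by arm.

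The cost is protocol wording and slightly more analysis work, with no extra subjects or visits. Bias from drop-out that depends on scores never observed is reduced but not removed.

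### Subjects withdrawn for an adverse event leave the analysis, and no visit worksheet shown or planned table captures adverse events by arm

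*Combined protocol and SAP*

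**What the plan says.** - **Who is withdrawn (16.1).** Besides those unable to complete the study tasks, subjects are withdrawn "if they experience an adverse event in which the investigator does not feel that the subjects should continue wearing the scleral lenses".
- **What happens to their data (16.3).** "The data from a subject that withdraws or is terminated from the study will not be included in the analysis". No exception is stated.
- **Who is analysed (5.2).** Only the first 30 eligible subjects who finish.
- **How adverse events reach the team (13.2).** "If a subject experiences an adverse event during the duration of the study, they will be instructed to call the study coordinator". An investigator then examines the subject if needed. Under 13.3 subjects are told which symptoms to watch for and whom to call.
- **What is collected and analysed.** Section 10.3 opens with "The following data will be collected in this study" and lists acuity, comfort questionnaire, keratograph, staining and lens fit. Adverse events are not on that list. They are also absent from the endpoints in 9.0, the statistical paragraph under 10.2 and the analysis text in 25.1.
- **Safety data monitoring.** The heading reads "15.0 Provisions to Monitor Data to Ensure the Safety of Subjects – N/A".
- **Product status (12.0).** "The Tangible Boost Replenishing system is not yet FDA approved but is undergoing approval".

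**The concern.** The kits are randomised at Visit 3, so the trial could give a small but unbiased by-arm description of harm. The withdrawal rule works against that. Subjects whose eyes react badly enough to stop lens wear are the most informative about harm, and all their data leave the analysis, including data recorded before they stopped.

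Two things are at stake. First, the trial would end with no planned account of adverse events or reasons for withdrawal by arm, for a product not yet approved. Second, two of the primary endpoints, staining and comfort, would describe only subjects who tolerated the lenses and solution well enough to finish. If poor tolerance were more common with one kit, the results for that kit would look better than they should.

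**Working it through.** **1. The plan's own figure.** Section 5.2 gives 30 analysed subjects and a combined loss of about 20%. 30 / (1 - 0.20) = 37.5, rounded up to 38, which lies inside the stated 35-40 and under the maximum of 40 in 5.1. Recruits outside the analysed 30 are 35 - 30 = 5, 38 - 30 = 8 or 40 - 30 = 10. This number mixes screening failures, losses before any kit is dispensed, later losses, and any finishers after the thirtieth. It is not a count of harms.

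**2. The rules in sequence.** In one arm, let R subjects be randomised, w withdrawn for an adverse event and d withdrawn for other reasons.
- By 16.1 and 16.3, at most R - w - d subjects are analysed.
- The number of adverse-event withdrawals among them is 0 for every value of w.
- Section 5.2 gives the same result independently, because none of the w subjects finishes. Amending 16.3 alone would leave 5.2 in force.

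**3. What is discarded, by time of withdrawal.**
- Before Visit 3: no kit has been dispensed, so nothing lost bears on Boost or placebo.
- After Visit 3, before Visit 4: the pre-treatment measurements from Visit 3.
- After Visit 4, before Visit 5: the Visit 3 measurements and the first post-treatment ones from Visit 4 (slit lamp, staining, CLDEQ-8, visual analogue scales).

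**4. Capture in subjects who continue.** The Visit 3, 4 and 5 worksheets record slit-lamp findings after lens removal, a staining score, CLDEQ-8, visual analogue scales, hours of wear that day and medication changes. Visits 3 and 4 also ask whether the lenses remain wearable. The patient surveys leave space for comments. None of these forms, nor the refitting form, asks about adverse events since the last visit.

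Section 13.1 names abrasion, stinging, redness, itching and irritation as foreseeable, and such events can clear before the next examination. The longest gap is the 60 days between Visits 4 and 5. The second treatment falls at its midpoint, about 60 - 30 = 30 days before Visit 5, with no visit then. The Visit 4 worksheet refers to a 30-day call log, described only as a reminder.

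**5. Effect on staining.** If a fraction f of an arm is withdrawn with mean score m_W, and finishers have mean m_C, the mean over all randomised is (1 - f) m_C + f m_W. The finishers-only mean differs from it by m_C - [(1 - f) m_C + f m_W] = -f (m_W - m_C). With higher scores meaning more staining, the finishers-only mean is too favourable whenever m_W exceeds m_C. The between-arm comparison is biased when this term differs between arms. The documents give no value for f, m_W or m_C.

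**6. A related inconsistency.** Section 16.1 frames adverse-event withdrawal around scleral lenses only, while 3.1 also enrols corneal lens wearers. The two passages must be reconciled, because 16.1 decides whose data 16.3 removes.

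**The case against.** The best defence is that this is a small pilot that the protocol calls low risk. The kit's ingredients are described in 12.0 as generally recognised as safe and the same as those of the approved coating, and exposure is two 30-minute soaks. Eyes are examined and staining scored at every scheduled visit, subjects are told whom to call, and an investigator sees those who need it. That is real safety cover for individuals, and ocular signs present at a visit in a continuing subject would be recorded. This part of the defence stands. It does not reach events that clear between visits, or subjects whose data are removed.

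Several stronger readings are tempting but unsupported:
- A reader might infer that 16.3 forbids reporting adverse events, or that withdrawals would be reported as a 0% rate. Section 16.3 governs the analysis only. It does not bar a separate listing, and no adverse-event rate is planned at all. The supportable statement is that no listing is planned.
- A reader might infer that harms are not captured anywhere. Capture is partial, as step 4 of the working shows. The Boost log, call log and usability datasheet are named but not shown, so the absence of an adverse-event item is established only for the worksheets in the document.
- A reader might express one or two Boost withdrawals as 1/15 or 2/15. Fifteen is half of the 30 finishers (30 / 2), and withdrawn subjects are not among them. With 15 finishers in an arm the denominators would be at least 15 + 1 = 16 or 15 + 2 = 17, and the allocation ratio is not stated.
- A confidence bound for zero events in 15 reflects the small sample under any retention rule. Taking 20% of 40, which is 8, as a measure of harm fails because that 20% pools screening failures with dropouts.
- A reader might treat the N/A against Section 15.0 as an error. It contradicts nothing else in the protocol. A periodic review of adverse events would be a reasonable preference, not a correction.

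**Conclusion.** The concern holds in this form. Sections 16.1 and 16.3 together, and 5.2 independently, remove every subject withdrawn for an adverse event from the analysis. No adverse-event question on the worksheets shown, and no planned by-arm table, makes up for it. This is a stated rule, not just missing detail, and it can bias the staining and comfort results.

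Certain from the text: adverse-event withdrawals in the analysed set are zero whatever happens, and data already recorded for those subjects are discarded. Not certain: how many such subjects there would be, whether they would differ by arm, and how many events in finishers would go unrecorded. No percentage should be attached, because the documents give no adverse-event rate and no allocation ratio. Any bias towards one kit also rests on the assumption that withdrawal for poor tolerance differs between arms.

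The change should be made. Confidence is medium, because some logs are not shown and a separate listing is not ruled out.

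**What to change.** 1. Add one line to the Visit 3, 4 and 5 worksheets and the unscheduled-visit form: any adverse event since last visit, with type, eye, onset and action taken.
2. Amend 16.3 and 5.2 together so that data up to withdrawal are kept for every randomised subject. Changing only one would leave two rules in conflict.
3. State in the analysis text that adverse events and reasons for withdrawal are tabulated by arm for everyone dispensed a kit, with events before Visit 3 listed separately because they precede Boost and placebo.
4. Reconcile the lens types named in 16.1 with those enrolled under 3.1.

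The cost is one line per form, short edits to two sections and one table, with no added visits. The downsides are slightly more data entry and event counts that may look less favourable.
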